#### ***10.1.4. Statistical Testing and Estimation***

No formal statistical analysis will be performed within the SAP specified analysis.

#### ***10.1.5. Handling of Dropouts or Missing Data***

In general, missing data will not be imputed and all summary statistics will be reported based upon observed data. For a limited number of summary presentations, missing data rules may be introduced. In particular, methods of handling incomplete dates for adverse events ([Section 10.8.2](#)) and incomplete dates for concomitant medications ([Section 10.5](#)) are presented. For any other data which has partial dates, which are required for use in time related calculations, these dates will be completed using a suitably conservative approach. Dates will be shown in subject Listings as they have been recorded.

#### ***10.1.6. Multiple Comparison/Multiplicity***

As no formal hypothesis testing is taking place, no alpha adjustments will be made to handle multiplicity.

#### ***10.1.7. Examination of Subgroups***

No subgroup analyses will be undertaken.

#### ***10.1.8. Model checking***

As no formal hypothesis testing is taking place no formal model checking will be required.

#### ***10.1.9. Software***

Data will be reported using SAS (version 9.4 or later).

### **10.1.10. Data Conversion (CDISC)**

For the reporting of this study both CDISC SDTM (SDTM version 1.7 and SDTM Implementation Guide version 3.3) and ADaM (ADaM version 2.1 and ADaM Implementation Guide version 1.1) standards will be applied.

## **10.2. Participant Disposition**

The number of subjects randomized, treated, received all doses as planned, received all doses expected, completed the Week 24 visit, and completed the study will be tabulated by treatment group, as well as the number who withdrew from the study and/or discontinue treatment early. The data on subject disposition and informed consent will be listed.

Note it was possible for participants to be rescreened. In order to maintain the link between screen failures and their subsequent rescreen records these will be displayed as XXXX/YYYY in all relevant listings (where screen failure data are displayed), where XXXX is the final screening number given to the subject and YYYY is the screening number under which the data being displayed was collected.

## **10.3. Protocol Deviations**

Subject data will be reviewed for major protocol deviations by a qualified clinical reviewer prior to database lock and unblinding, at the BDRM at the time of the Final Analysis. All protocol deviations will be listed.

## **10.4. Demographic and other Baseline Characteristics**

The Safety Population will be used in all presentations of demographic and baseline data. No statistical testing will be used to compare treatments for different baseline characteristics.

### **10.4.1. Demographics**

Demographic variables at screening (sex, age, ethnicity, race, height (cm), weight (kg), and body mass index (BMI [g/m^2]), will be summarized by treatment group and across all subjects.

### **10.4.2. Other Baseline Characteristics**

Smoking history, alcohol consumption and drugs of abuse information will all be listed

### **10.4.3. Medical History**

All medical history will be coded using MedDRA, Version 25.0 (March 2022), summarized by treatment group and listed.

Asthma medical history will also be listed, as will allergy history and past and planned surgical procedures

## **10.5. Prior and Concomitant Medications**

All medication terms will be coded using the World Health Organisation (WHO) Drug Dictionary Enhanced (WHO Drug Global, version March 1, 2022).

Background asthma medications are defined as medications taken for asthma at a stable dose during at least 3 months prior to randomization.

Other medications will be assigned as being prior to or concomitant with the treatment, based on the start and stop dates of the medication and the date of first dose of study treatment. If the medication stop date is before the date of first dose of study treatment, the medication will be assigned as being prior to study treatment. In all other situations, the medication will be assigned as being concomitant with study treatment.

Note: Start and Stop times will not be used for determining if a medication is concomitant or not.

All background asthma medications will be summarized, including the duration of exposure. Background asthma medications will also be listed, along with any changes from the stable dose that occur during the study.

All concomitant medications will be summarized by ATC class (Level 2) and preferred base name (WHO Code 01001). All medications will be listed.

## **10.6. Pregnancy**

The results of pregnancy tests, both urine and serum, carried out throughout the study will be listed for all females. The results of the follicle stimulating hormone test will also be listed for the females who meet the post-menopausal criteria.

## **10.7. Other Baseline/Screening Tests**

Drugs of abuse screening results will be listed, as will the results of any alcohol breath tests and urine cotinine tests.

## **10.8. Investigational Product Exposure**

For each cohort the number and percentage of participants receiving each possible number of doses and injections will be tabulated. The details of each injection, including location and the reasons for incomplete and interrupted injections will be listed.

Planned Compliance will be calculated as: (the actual number of injections received / the number of injections planned given the assigned dosing regimen) \* 100.

Expected Compliance will be calculated as: (the actual number of injections received / the expected number of injections given the assigned dosing regimen and the conduct of the trial) \* 100.

The expected compliance accounts for the hold on dosing that occurred during the running of the trial during which subjects were not expected to have received any doses of study treatment, both will be listed.

## **10.9. Pharmacokinetic Analysis**

The pharmacokinetic analysis will be reported separately, the specifications will be outlined within the PK analysis plan. This will include the identification of the PK population, the summary of the PK concentrations and PK parameters as well as the investigation of dose proportionality.

## **10.10. Immunogenicity Analysis**

The immunogenicity analysis of neutralising antibodies and anti-drug antibodies will be reported separately, the specifications will be outlined within the PK analysis plan.

## **10.11. Pharmacodynamic Analysis**

All Pharmacodynamic analysis will use the Pharmacodynamic population.

### **10.11.1. Biomarkers**

The biomarkers collected in the study include cytokines (IL-5, IFN λ, IP-10, TSLP, eotaxin-3, TARC and lab parameters (Eosinophils, Total IgE and C-reactive protein). Receptor occupancy evaluated by flow cytometry, considered as a biomarker for target engagement, is also included.

All biomarkers, with the exception of the flow cytometry biomarker, will be summarized by visit as absolute values, change from baseline and percentage change from baseline, by treatment group. Any scheduled pre-baseline data will also be summarized by visit and treatment group.

Flow cytometry based evaluation of receptor occupancy (free receptors) will be calculated as the difference between the signal intensity (measured as % of TSLPR+ CD14+ cells) of the test sample and an aliquot of the same sample incubated ex vivo with saturating levels of UPB-101 prior to adding the detection antibody. The receptor occupancy will then be summarized at each visit, along with the percentage of free receptors, where;

% free receptors at any timepoint (t) = (difference between signal intensity at timepoint (t) / difference between signal intensity at baseline )\* 100.

For negative % Free Receptors, set the value to 0. For % Free Receptors greater than 100%, set the value to 100%.

For all biomarkers the baseline will be the last non-missing result prior to first dose.

Any data that is below the limit of quantification will be replaced with zero before summarising but will be listed as '<BLQ'.

A mean plot of the biomarker results over time will be displayed, where the plots will display the mean at each visit +/- the standard error, with a line per treatment group.

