### 7.3. Exploratory Endpoints

The exploratory endpoints include:

AEs, SAEs, pregnancy tests, and changes from baseline in physical examinations, clinical laboratory assessments, vital signs, and ECGs. Subject withdrawals, early termination, and dosing compliance are also assessed. Data collected from Baseline through Week 32 are included (data up to Week 24 are examined as part of the primary endpoints analysis). These endpoints are evaluated in the Safety Population.

UPB-101 ADAs, presence of neutralizing antibodies (Nabs) and serum UPB-101 concentrations and analyses including  $C_{max}$ ,  $t_{max}$ ,  $AUC_{tau}$ . Data collected from Baseline through Week 32 in the PK Population are included (data up to Week 24 are examined as part of the secondary endpoints analysis).

FeNO and blood eosinophil numbers from Baseline through Weeks 24 and 32. Total IgE; IL-5, IL-13, IL-17A, interferon gamma (IFN  $\lambda$ ), IFN  $\lambda$ -induced protein 10 (IP-10), TSLP, eotaxin-3, tryptase, carboxypeptidase, thymus activation regulated chemokine (TARC), C-reactive protein (CRP) concentrations; and flow cytometric assessments of phosphorylated signal transducer and activator of transcription (pSTAT) and receptor occupancy will be evaluated from Baseline through Weeks 24 and 32. These PD markers are evaluated in the PD Population.

Clinician Global Impression of Change (CGI-C) and Subject Asthma Control Questionnaire (ACQ-7) from Baseline through Weeks 24 and 32. These PD markers are evaluated in the PD Population.

Forced expiratory volume in 1 second (FEV1) from Baseline through Weeks 24 and 32. These PD markers are evaluated in the PD Population.

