#### 10.1.3. Data Presentation

The full list of TFLs to be produced for the final study analysis are shown in [Section 13](#), and the specific format and content of each data Table/Listing presentation is shown in [Section 14](#).

Summary Tables and Figures will be presented by treatment group (and also for an Overall column including all subjects, for selected data presentations). Within all Tables and Figures values for the treatment groups will be labelled as follows:

- [REDACTED] mg [REDACTED]
- [REDACTED] mg [REDACTED]

- [REDACTED] mg [REDACTED]
- [REDACTED] mg [REDACTED]
- Placebo and/or
- Screen Failures

An Overall column may be included in the disposition, and selected safety outputs which will include all treatment groups (Active and Placebo). Generally, the placebo groups will be pooled across all cohorts however, for some summaries placebo may be summarized according to dosing regimen (e.g. Placebo [REDACTED], Placebo [REDACTED] ) or treatment group (e.g. Placebo [REDACTED]).

For screen failures, data is only expected in a selection of datasets. The data collected within these datasets will be included in the relevant listings only. Additional data that may have been collected for screen failures, in error, will not be displayed in the participants listings. They will not be included in any summary tables.

For selected outputs the dosing regimen may be used in the summaries where cohorts of the same dosing regimen (i.e. [REDACTED], [REDACTED] ) will be grouped together, similarly cohorts may be grouped together by treatment group if there are multiple cohorts with the treatment group (e.g. [REDACTED] [REDACTED]), or summaries may be produced combining all of the active groups together. The ordering of treatment groups shown here represents the order in which they will appear in outputs.

The scheduled protocol visits will be labelled in (applicable) report presentations as follows:

- Screening: Visit 1
- Screening: Visit 2
- Screening: Visit 3
- Day 1
- Day X (where X is the protocol specified Day, to be included within summary Table)
- Week X (where X is the protocol specified study Week, to be included within summary Table)

Generally, the summaries will be produced by Day, although in some cases it may be preferable to summarize by Week. This will be specified within each of the shells, as appropriate.

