Note that the Baseline label will be used in some summaries, where Baseline will consist of data collected at the screening visits, on Day 1 pre-dosing or unscheduled assessments prior to dosing (if they are the last non-missing assessment). The actual Baseline definition will be provided in the section relevant for each endpoint.

Unscheduled visit data will be labelled as “Unscheduled” together with a date in data Listings. Unscheduled data will not be used in the summary tables unless otherwise agreed at the BDRM.

Where duplicate information is collected in both the database and in the vendor data transfer(s) (e.g., sampling date and time) this information will be reconciled by data management and then the information from the database will be included in subject Listings.

All variables will be listed to the same number of decimal places as reported. Descriptive statistics for all endpoints that are continuous data will have the following summary statistics presented in the following order: n, (arithmetic) mean (rounded to one more decimal place than recorded), geometric mean (for pre-specified endpoints only; rounded to one more decimal place than recorded), standard

deviation (rounded to two more decimal places than recorded), geometric standard deviation (for pre-specified endpoints only; rounded to two more decimal places than recorded), standard error (for pre-specified endpoints only; rounded to two more decimal places than recorded), median (rounded to one more decimal place than recorded), lower and upper quartiles (rounded to one more decimal place than recorded), minimum (as recorded), and maximum (as recorded).

Note: for endpoint(s) that require a geometric mean to be produced, and those endpoint(s) can have raw values of 0 (zero), the geometric mean calculation will add an appropriate constant value to all raw values prior to logging and will subtract that constant value from the final calculated anti-logged mean. The constant value used will be documented in the footnote of the tables. An example of such a calculation is shown below:

Geometric Mean = anti-log {mean (logged (base 10) endpoint values + 1)} - 1

Categorical variables will be summarized using proportions (counts and percentages). The specific approach to calculating percentages (relevant denominator) is detailed within each (relevant) Table template ([Section 14](#)).

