### 13.2. List of Tables

The columns Final and Admin Analysis identify the tables that will be produced for each of the Final Analysis and Administrative Interim Analysis, respectively.

Table Number	Table Title	Final	Admin Analysis
14.1.1	Subject Disposition – All Subjects	X	X
14.1.2	Demography and Baseline Characteristics – Safety Population	X	X
14.1.3	Medical History – Safety Population	X	
14.1.4.1	Concomitant Medications – Safety Population	X	
14.1.4.2	Background Asthma Medications – Safety Population	X	
14.1.5	Investigational Product Exposure – Safety Population	X	X
14.2.3.1.1	Biomarkers: Cytokines Change from Baseline Summary – Pharmacodynamic Population	X	X
14.2.3.1.2	Biomarkers: Cytokines Percentage Change from Baseline Summary – Pharmacodynamic Population	X	X
14.2.3.2.1.1	Biomarkers: Eosinophils Change from Baseline Summary – Pharmacodynamic Population	X	X
14.2.3.2.1.2	Biomarkers: Eosinophils Percentage Change from Baseline Summary – Pharmacodynamic Population	X	X
14.2.3.2.2.1	Biomarkers: Other Labs Change from Baseline Summary – Pharmacodynamic Population	X	X (IgE only)
14.2.3.2.2.2	Biomarkers: Other Labs Percentage Change from Baseline Summary – Pharmacodynamic Population	X	X (IgE only)
14.2.3.3.1	Biomarkers: Flow Cytometry Change from Baseline Summary – Pharmacodynamic Population	X	X
14.2.3.3.2	Biomarkers: Flow Cytometry Percentage of Baseline Summary – Pharmacodynamic Population	X	X
14.2.3.4.1.1	Biomarkers: FeNO Change from Baseline Summary – Pharmacodynamic Population	X	X
14.2.3.4.1.2	Biomarkers: FeNO Percentage Change from Baseline Summary – Pharmacodynamic Population	X	X

Table Number	Table Title	Final	Admin Analysis
14.2.3.4.2.1	Biomarkers: Other Spirometry Change from Baseline Summary – Pharmacodynamic Population	X	X (FEV1 only)
14.2.3.4.2.1	Biomarkers: Other Spirometry Percentage Change from Baseline Summary – Pharmacodynamic Population	X	X (FEV1 only)
14.2.4.1.1	CGI-C Summary – Safety Population	X	
14.2.4.1.2	CGI-C Categorical Summary – Safety Population	X	X
14.2.4.2.1	ACQ-7 Summary – Safety Population	X	X
Safety			
14.3.1.1	Injection Site Reactions Summary – Safety Population	X	X
14.3.1.2	Injection Site Reactions by Location – Safety Population	X	
14.3.1.3	Injection Site Reactions - Proportion with Reactions – Safety Population	X	
14.3.2.1.1	Overall Summary of Treatment Emergent Adverse Events up to Week 24 – Safety Population	X	

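### Capping % free receptors at 0 and 100 before summarising biases the mean and SD in Table 14.2.3.3.2 and compresses the active-placebo contrast

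*SAP*

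**What the plan says.** SAP 10.11.1 treats receptor occupancy by flow cytometry as the biomarker for target engagement. Free receptors are measured as a signal difference between a test sample and an aliquot saturated with UPB-101. The percentage at a visit is that difference over the baseline difference, times 100. The rule that follows changes the value itself, not only its display: "For negative % Free Receptors, set the value to 0. For % Free Receptors greater than 100%, set the value to 100".

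The baseline is a single result: "For all biomarkers the baseline will be the last non-missing result prior to first dose".

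The percentage is summarised at each visit. SAP 13.2 lists it as Table 14.2.3.3.2, "Biomarkers: Flow Cytometry Percentage of Baseline Summary", marked for both the final and the administrative interim analysis. A companion table, 14.2.3.3.1, is "Biomarkers: Flow Cytometry Change from Baseline Summary". For biomarker plots, 10.11.1 says "the plots will display the mean at each visit +/- the standard error, with a line per treatment group". Figure 14.2.3 is the flow cytometry mean plot (final analysis only), and the SAP does not say whether it shows the percentage or the signal difference.

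The SAP asks for neither an unclipped summary of the percentage nor a count of clipped values. Section 11 gives no reason for the rule.

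**The concern.** When nothing has changed in a subject, the visit result and the baseline result are two noisy readings of the same quantity. Their ratio is as likely to exceed 100 as to fall short of it. The cap removes the error on the upper side and keeps the error on the lower side, so it turns noise into a downward bias and hides part of the spread. The floor at 0 does the reverse when receptors are fully occupied. Values in the middle of the range are hardly touched.

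The stake is how the target-engagement table reads. Judged against its natural reference of 100, a placebo or washed-out group looks slightly occupied and more homogeneous than it is. The difference between active and placebo looks smaller than it is. Protocol 1.7 (Study Posology) says PD data from the long Observation Period will inform modelling of doses and intervals. It does not say whether clipped percentages would be used there.

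**Working it through.** The plan states no SD or CV for this endpoint, so there is no figure of its own to reproduce.

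**Inputs.** From the documents: the ratio, the 0 and 100 limits and the single baseline (SAP 10.11.1); 6 active and 2 placebo subjects per cohort (SAP 8); 3 to 5 cohorts (Protocol 3.1.1). On placebo, SAP 10.1.3 says "Generally, the placebo groups will be pooled across all cohorts", which gives 2 × 3 = 6 to 2 × 5 = 10 subjects. Assumed: independent errors with the same CV (5, 10 or 20%) on the visit and baseline differences.

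**Step 1: direction, with no CV needed.** If visit and baseline results are exchangeable and continuous, P(ratio > 100) = 0.5. The clipped group mean is below 100 whenever at least one value is below 100, with probability 1 − 0.5^n:
- n = 6: 98.4%
- n = 8: 99.6%
- n = 10: 99.9%

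This gives the sign of the bias, not its size, and assumes every subject has a result.

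**Step 2: size when nothing has changed.** With lognormal errors, log(ratio) is normal with mean 0 and variance τ² = 2·ln(1 + CV²). Then:
- clipped mean = 100·[0.5 + exp(τ²/2)·Φ(−τ)]
- clipped second moment = 100²·[0.5 + exp(2τ²)·Φ(−2τ)]
- unclipped mean = 100·exp(τ²/2), and unclipped SD = that mean × √(exp(τ²) − 1)

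For CV 10%, τ = 0.1411, exp(τ²/2) = 1.0100 and Φ(−τ) = 0.4439. The clipped mean is 100·(0.5 + 1.0100 × 0.4439) = 94.8.

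| Assumed CV | Unclipped mean (SD) | Clipped mean (SD) | SD ratio |
|---|---|---|---|
| 5% | 100.3 (7.1) | 97.3 (3.9) | 0.55 |
| 10% | 101.0 (14.3) | 94.8 (7.3) | 0.51 |
| 20% | 104.0 (29.7) | 90.5 (13.0) | 0.44 |

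Simulation with lognormal errors agrees, and normal errors give nearly the same means. If instead the percentage itself has symmetric normal error with SD s around 100, the clipped mean is 100 − 0.399s and the SD ratio is 0.58.

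**Step 3: partly washed-out groups.** With a true mean of 90 and normal SD 10, 20 or 30, the SD ratio is 0.87, 0.74 or 0.69. The shrinkage is clearly smaller than at 100.

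**Step 4: full occupancy.** With a true value of 0 and noise SD of 5 or 10% of baseline, the floor lifts the mean to about 0.399 × 5 = 2.0 or 0.399 × 10 = 4.0. At CV 20% in the baseline these become 2.1 and 4.2.

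**Step 5: contrast.** A true 100-point difference between no change and full occupancy reads:
- CV 5%: 97.3 − (2.0 to 4.0) = 93 to 95
- CV 10%: 94.8 − (2.0 to 4.0) = 91 to 93
- CV 20%: 90.5 − (2.1 to 4.2) = 86 to 88

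At a true 50% free, clipping moves the mean by 0.1 point or less.

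**Step 6: medians.** In simulated no-change groups of 6, the sample median of the clipped values averages 98.5, 97.1 and 94.5, against 100.1, 100.3 and about 101 unclipped. The clipped upper quartile in the population is exactly 100 (unclipped 104.9, 110.0, 120.8).

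**Step 7: SE, only if Figure 14.2.3 plots the percentage.** In simulated no-change groups of 6, the average SE falls from 2.75, 5.54 and 11.3 to 1.43, 2.72 and 4.90. Mean + 1 SE then lies wholly below 100 in 90% of groups, against 14 to 17% unclipped.

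**The case against.** The case for leaving the rule alone has several parts.

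- **Low stakes.** SAP 7.3 lists "flow cytometric assessments of phosphorylated signal transducer and activator of transcription (pSTAT) and receptor occupancy" among the exploratory endpoints, and 10.1.4 plans no formal analysis. This stands: no error rate is affected, only the reading of a descriptive table.
- **Placebo has the same offset.** This also stands. A reader might infer that clipping manufactures target engagement. It does not: judged against placebo, a group back at baseline shows no excess, and the contrast errs toward too little engagement.
- **Other summaries exist.** Table 14.2.3.3.1 covers change from baseline, and the clipping rule names only the percentage, but that table is not on the percentage scale. SAP 10.1.3 already asks for the "median (rounded to one more decimal place than recorded), lower and upper quartiles". For this percentage they would be taken from clipped values, so they help only in part. A maximum of exactly 100 would at least hint at the cap.
- **The error bars.** A reader might infer that the plotted standard errors are halved. The documents do not support that as it stands. SAP 10.1.3 gives the SE only for pre-specified endpoints, the sample layout in 13.1 shows SD, and 10.11.1 specifies the SE only for plots. Figure 14.2.3 may not show the percentage at all.
- **Washout.** A reader might also infer that active groups will be shown as falsely occupied late in follow-up. Half-life and predicted exposures are redacted, so nothing visible shows that any active group returns to baseline by Week 32. Placebo is the certain case.
- **Values above 100% are impossible.** True of occupancy, but not of a ratio of two measurements with error.

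**Conclusion.** The point holds as a modest reporting correction. The direction of the bias follows from the SAP's own rule and needs only that visit and baseline readings are exchangeable when nothing has changed. Its size is not in the documents. At assumed CVs of 5 to 20% with independent, equal errors, the no-change mean is about 3 to 10 points below 100 and the SD is roughly half its unclipped value. Those SD figures belong to a group truly at 100 and overstate the shrinkage for a partly washed-out group. The real assay's error structure, built on a difference of two cell percentages from the same sample, may differ. Any effect on plotted standard errors depends on what Figure 14.2.3 shows.

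**What to change.** In SAP 10.11.1 and Table 14.2.3.3.2, summarise unclipped % free receptors, led by the median and quartiles. The median should lead because the unclipped arithmetic mean runs slightly high (100.3, 101.0 and 104.0 at the assumed CVs) and, in groups of 6, one small baseline value could dominate it. Show the number of values below 0 and above 100 by visit and treatment group. Keep clipped values only in a labelled listing (16.2.6.3). State which quantity Figure 14.2.3 plots; if it is the percentage, plot the unclipped median with quartiles instead of mean and SE.

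The cost is SAP wording plus changes to one table, one figure and one listing; no new data are needed. The downside is that some values outside 0 to 100 will appear, and a footnote must explain that they reflect measurement error. The Section 14 shells are not in the available copy, so an existing footnote on clipping cannot be ruled out and should be checked first.
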